7.1.6 Suspected Unexpected Serious Adverse Reaction (SUSAR)

SUSARs are SAEs that are at a minimum possibly related to the study agent and are unexpected (i.e., not listed in the investigator brochure). SUSARs will be collected and expeditiously reported to CAs and IECs according to applicable regulatory requirements.

7.1.7 Toxic Death

Any death to which drug toxicity is thought to have made a contribution should be notified to [REDACTED] at once. [REDACTED] will notify the DEC and sponsor immediately.

7.1.8 Pregnancy

In this trial, pregnancies occurring during participation (including pregnancies of partners of male subjects) are not considered as an AE per se, but they must be reported to the sponsor using the trial Pregnancy Reporting Form, according to the rules described in [Section 7.2.3](#).

The CA and IEC will be informed on these pregnancies.

Pregnancies must be followed-up to determine outcome (including spontaneous miscarriage, elective termination, normal birth, or congenital abnormality) and status of mother and child, even if the subject was discontinued from the trial. Pregnancy complications, elective terminations for medical reasons and spontaneous miscarriages must be reported as SAEs.

7.2 Monitoring, Reporting, and Documentation of Adverse Events (AEs)

7.2.1 Monitoring of AEs

Subjects will be monitored for AEs and Events of Clinical Interest (ECIs) from the time of ICF signature until the FU visit (or until EoT, if it occurs more than 30 days after the last CyPep-1 administration for Phase I and Arms A and C and D; for Arm B refer to Section 7.2.1.3). After the FU visit (or EoT visit, if it occurs more than 30 days after the last CyPep-1 administration), only ongoing AEs or SAEs related to CyPep-1 administration will be collected.

For all phases and arms, AEs will be assessed using CTCAE v5.0 ([Appendix C](#)), assessments will include start and stop dates, severity, relationship to CyPep-1 and / or pembrolizumab, outcome and action taken.

At every trial visit, subjects will be asked whether they have experienced or are experiencing any medically related changes in their health. They will also be asked if they have been hospitalized, had any accidents, used any new medications/therapies, or changed concomitant medication regimens (both prescription and over the counter medications).

In addition, for all subjects with any remaining CyPep-1 and / or pembrolizumab-related AEs at the last follow-up visit after the last CyPep-1 intratumoral administration, AE information needs to be collected until:

- The symptom subsides or stabilizes;
- Any clinically relevant abnormal laboratory value has returned to baseline;
- There is a satisfactory explanation other than the trial medication for the change(s) observed; or
- Death, in which case an autopsy report should be supplied to [REDACTED], if performed.

7.2.1.1 Events of Clinical Interest (Arm B)

Selected non-serious and serious adverse events are also known as Events of Clinical Interest (ECI) and must be reported to the Sponsor within 24 h of awareness.

Events of clinical interest for this trial include:

1. an overdose of Sponsor's product, as defined in [Section 7.2.1.2](#)
2. an elevated AST or ALT lab value that is greater than or equal to 3X the upper limit of normal and an elevated total bilirubin lab value that is greater than or equal to 2X the upper limit of normal and, at the same time, an alkaline phosphatase lab value that is less than 2X the upper limit of normal, as determined by way of protocol-specified laboratory testing or unscheduled laboratory testing.*

*Note: These criteria are based upon available regulatory guidance documents. The purpose of the criteria is to specify a threshold of abnormal hepatic tests that may require an additional evaluation for an underlying etiology. The trial site guidance for assessment and follow up of these criteria can be made available. It may also be appropriate to conduct additional evaluation for an underlying etiology in the setting of abnormalities of liver blood tests including AST, ALT, bilirubin, and alkaline phosphatase that do not meet the criteria noted above. In these cases, the decision to proceed with additional evaluation will be made through consultation between the study investigators and the Sponsor Clinical Director. However, abnormalities of liver blood tests that do not meet the criteria noted above are not ECIs for this trial.

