The safety and tolerability of at least two dose levels of CyPep-1, namely the RP2D and the dose immediately below that, are planned to be evaluated when CyPep-1 is administered intratumorally using ultrasound guidance to one metastatic lesion in the liver. The two dose levels are planned to be investigated adhering to the 3+3 design and will follow the procedures as described for the dose escalation (Phase I) (Section 3.1). The first three subjects will receive CyPep-1 at the lower dose level and each subject will be observed for 24 h before CyPep-1 administration to a next subject (cohort 4). After the third subject at that dose finished the DLT observation period of 6 weeks (5 weeks CyPep-1 treatment plus 1 week safety follow-up), the DEC will decide on the start of the cohort to be administered at RP2D based on the review of the safety data (cohort 5). In the absence of any DLTs in the first 3 subjects, the 24-h observation period before start treatment of the next subject is not applicable. After the DLT observation period for the first three subjects at RP2D for CyPep-1 and the review of all safety data, the DEC will recommend on the inclusion of all remaining subjects. Should a DLT be observed in the first three subjects at the RP2D of CyPep-1, an additional three subjects in this dose group will be included. In case that two or more subjects experience DLTs at RP2D of CyPep-1, a recommendation to dose de-escalate and to what dose and how to continue Arm C will be made by the DEC.

Phase IIa – dose expansion melanoma subjects (Arm D):

The safety and tolerability of CyPep-1 at RP2D will be further evaluated with focus on assessing efficacy signals of CyPep-1 monotherapy in up to 30 subjects with melanoma. Although safety information will be collected, there will not be a formal DLT observation period. The dosing scheme starts with a once weekly (QW) CyPep-1 administration until the second iRECIST/itRECIST assessment at week 16, followed by a Q2W dosing scheme.

As part of the continuous safety monitoring of the trial, reports with cumulative safety data of Arm D subjects will be shared with all investigators, competent authorities, and ethical committees of countries where the trial is conducted at the following time points:

- After the first three subjects completed three weeks of treatment with CyPep-1.
- After the first three, six, and 12 subjects completed six weeks of treatment with CyPep-1.

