3.1.2 Dose Limiting Toxicities / Treatment Limiting Toxicities

A DLT is defined by the occurrence of any of the following toxicities according to CTCAE v5.0 during treatment Cycle 1 and that are considered by the investigator to be possibly, probably, or definitely related to CyPep-1:

3. Any Grade ≥ 3 AEs of any etiology, except:
 - o Nausea, vomiting, or diarrhea will be considered a DLT only if it persists at Grade ≥ 3 for > 3 days despite adequate supportive care measures. At the investigator's discretion, subjects who experience nausea, vomiting, or diarrhea after receiving CyPep-1 may receive antiemetic or anti-diarrheal medication prior to subsequent doses of CyPep-1.
 - o Isolated laboratory abnormalities Grade ≥ 3 (not present at baseline) that resolve to Grade ≤ 1 in ≤ 7 days without clinical sequelae or need for therapeutic intervention.
 - o Fatigue Grade ≥ 3 for ≤ 7 days.
 - o For Phase I, Arms A and C:
 - Alanine amino transferase (ALAT) or Aspartate amino transferase (ASAT) toxicities:
 - ALAT or ASAT $> 5 \times$ upper limit of normal (ULN) ($> 7.5 \times$ ULN for subjects with liver metastases), unless greater than 14 days.
 - ALAT or ASAT $> 5 \times$ ULN ($> 7.5 \times$ ULN for subjects with liver metastases) accompanied by an elevation in total bilirubin of $> 2.5 \times$ ULN (not explained by obstruction), regardless of duration, will be considered a DLT.
4. Any other toxicity occurring at any time during the trial that in the view of the participating investigators and the medical monitor represents a clinically significant hazard to the subject.

All TLTs will be graded using NCI CTCAE v5.0 based on the investigator assessment. The TLT window of observation will be during Cycle 1.

The occurrence of any of the following toxicities during Cycle 1 will be considered a TLT, if assessed by the investigator to be possibly, probably, or definitely related to trial treatment administration.

1. Grade 4 nonhematologic toxicity (not laboratory).
2. Grade 4 hematologic toxicity lasting ≥ 7 days, except thrombocytopenia:
 - Grade 4 thrombocytopenia of any duration
 - Grade 3 thrombocytopenia associated with clinically significant bleeding

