7.2.1.2 Treatment of Overdose (Arm B)

For this study, an overdose of pembrolizumab will be defined as any dose of 1000 mg or greater.

No specific information is available on the treatment of overdose of pembrolizumab. In the event of overdose, the subject should be observed closely for signs of toxicity. Appropriate supportive treatment should be provided if clinically indicated.

7.2.1.3 Time Period and Frequency for Collecting AE, SAE and Other Reportable Safety Event Information (Arm B)

Specific considerations on safety reporting for Arm B are summarized below:

- All AEs, SAEs and other reportable safety events that occur after the consent form is signed but before treatment /allocation must be reported by the investigator if the participant is receiving placebo run-in or other run-in treatment, if the event cause the participant to be excluded from the study, or is the result of a protocol-specified intervention, including but not limited to washout or discontinuation of usual therapy, diet, or a procedure.
- All AEs or ECIs (Events of Clinical Interest) from the time of treatment/ allocation through 30 days following cessation of study treatment must be reported by the investigator.
- All AEs meeting serious criteria, from the time of treatment/ allocation through 90 days following cessation of study treatment, or 30 days following cessation of study treatment if the participant initiates new anticancer therapy, whichever is earlier must be reported by the investigator.
- All pregnancies and exposure during breastfeeding, from the time of treatment/ allocation through 120 days following cessation of study treatment, or 30 days following cessation of study treatment if the participant initiates new anticancer therapy must be reported by the investigator.
- Additionally, any SAE brought to the attention of an investigator at any time outside of the time period specified above must be reported immediately to the Sponsor if the event is considered to be drug-related.

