The number and percentage of subjects with NCI-CTCAE toxicities will be tabulated by laboratory evaluation with defined NCI-CTCAE grading at each visit and at any time (including unscheduled visits) for hematology, biochemistry, coagulation and thyroid function. Subjects with missing values post-baseline will be excluded from the summary. The denominator for percentages will be the number of subjects with at least one post-baseline assessment for the laboratory parameter in question.

Hematology, biochemistry, coagulation and thyroid function shift tables displaying the shift from baseline to the maximum value of NCI-CTCAE grade will be presented (see Section [8.16](#) for details on shift table creation).

Potential hepatotoxicity will be evaluated by presenting shifts from baseline to worst post-baseline NCI-CTCAE grade for ALT, AST, total bilirubin, alkaline phosphatase and gamma-glutamyl transferase split by baseline status (normal at baseline, abnormal at baseline). If any of the parameters of interest is abnormal at baseline, the subject is considered to belong to the abnormal at baseline group. Only subjects who have normal results for all parameters of interest are considered to belong to the normal at baseline group. NCI-CTCAE Grade 1 or above is considered abnormal for the purpose of this analysis.

Potential hepatotoxicity will additionally be assessed by similar table but splitting by liver metastasis at baseline (no metastasis, metastasis). Finally, a potential hepatotoxicity table by baseline liver metastasis and iRECIST best overall response (iCR + iPR + iSD or UPD + iCPD + NE) will be created.

Mean ($\pm \text{SD}$) hematology and biochemistry laboratory results will be plotted over time by cohort/arm for SAF. Parameters measured only before treatment start will be excluded from the plots.

Mean ($\pm \text{SD}$) ALT, AST, total bilirubin, and alkaline phosphatase results will be plotted over time for SAF by liver metastasis at baseline (no metastasis, metastasis) and separately by baseline result for parameter of interest (normal at baseline, abnormal at baseline; by parameter); subjects from all cohorts/arms will be pooled for this analysis (i.e., presenting only for Total: Phase I + IIa).

All laboratory parameters will be provided in subject data listings for all subjects, a separate listing including CTCAE Grade 3 or higher laboratory abnormalities will be created.

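### The scope of Events of Clinical Interest is ambiguous outside Arm B, so some concurrent ALT/AST and bilirubin rises in the liver-injected Arm C have no clear 24 h route, and no SAP table counts them

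*Protocol*

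**What the plan says.** Protocol 7.2.1 opens: "Subjects will be monitored for AEs and Events of Clinical Interest (ECIs) from the time of ICF signature until the FU visit". The same sentence names Phase I and Arms A, C and D when it fixes the end of the window, and sends Arm B to 7.2.1.3. Protocol 5.6 asks for concomitant medication given during ECIs to be recorded and limits this to no arm.

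The definition comes only under "7.2.1.1 Events of Clinical Interest (Arm B". Its text, however, begins "Events of clinical interest for this trial include", and the events "must be reported to the Sponsor within 24 h of awareness". Criterion 2 is AST or ALT at least 3 x ULN with total bilirubin at least 2 x ULN and, at the same time, alkaline phosphatase below 2 x ULN.

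In Arm C, CyPep-1 is "administered intratumorally using ultrasound guidance to one metastatic lesion in the liver" (Protocol 3.1). The DLT list in 3.1.2 has a combined rule for Phase I and Arms A and C: ALAT/ASAT above 5 x ULN (above 7.5 x ULN with liver metastases) together with total bilirubin above 2.5 x ULN, "not explained by obstruction), regardless of duration, will be considered a DLT".

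SAP 11.4 states: "Potential hepatotoxicity will be evaluated by presenting shifts from baseline to worst post-baseline NCI-CTCAE grade for ALT, AST, total bilirubin, alkaline phosphatase" and gamma-glutamyl transferase. These tables are split by baseline status, by liver metastasis, and by liver metastasis with best response. SAP 11.1 restates the monitoring sentence without ECIs.

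**The concern.** Safety is the primary objective, and Arm C exists to test injection into the liver. The protocol treats a combined aminotransferase and bilirubin rise without a matching alkaline phosphatase rise as urgent enough for a 24 h report. Whether an Arm C site owes that report depends on whether it follows the heading of 7.2.1.1 or the body of 7.2.1.1 together with 7.2.1 and 5.6. The passages give no way to decide.

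The analysis has a matching gap. The signal is defined by values that coincide, but the SAP tables treat the analytes one at a time. The report could therefore show every liver parameter without stating how many subjects met the protocol's own combined criterion. For ECI counts this holds in Arm B too, where the definition plainly applies.

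**Working it through.** No sample size or error rate is involved. The check sets the passages side by side.

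**1. ECI criterion 2 against the combined DLT rule.** All Arm C subjects have liver metastases, so the 7.5 x ULN limit applies.

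| | ECI criterion 2 (7.2.1.1) | Combined DLT rule (3.1.2) |
|---|---|---|
| AST or ALT | >= 3 x ULN | > 7.5 x ULN |
| Total bilirubin | >= 2 x ULN | > 2.5 x ULN, obstruction excluded |
| ALP | < 2 x ULN | no condition |
| Timing | not limited to Cycle 1 | Cycle 1 |
| Relatedness | not required | at least possibly related |

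A rise that meets criterion 2 misses the combined DLT rule if any of these is true:

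- AST/ALT lies between 3 and 7.5 x ULN, or bilirubin between 2 and 2.5 x ULN;
- it occurs after Cycle 1;
- it is judged unrelated.

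The general Grade 3 clause of 3.1.2 may still catch part of the first group. For example, bilirubin above 3 x ULN is Grade 3 from a normal baseline (Protocol Table 3, footnote b). That clause also requires Cycle 1 and relatedness.

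**2. Worked example.** Take ALT 4 x ULN, bilirubin 2.2 x ULN and ALP 1.5 x ULN on one date, from normal baselines.

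- Criterion 2: 4 >= 3, 2.2 >= 2 and 1.5 < 2, so it is met. In Arm B this is a 24 h report.
- Combined DLT rule: 4 is not above 7.5 and 2.2 is not above 2.5, so it is not met.
- Grade: Table 3, footnote a, puts ALT above 3 to 5 x ULN and bilirubin above 1.5 to 3 x ULN in Grade 2. The event is therefore also absent from the Grade 3 or higher TEAE rows (SAP 11.1.3) and from the Grade 3 or higher laboratory listing (SAP 11.4).

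**3. What the shift tables show.** Let subject X have the values above on one date. Let subject Y reach ALT 4 x ULN at one visit and bilirubin 2.2 x ULN at a later one, each with the other analyte normal. Both have worst ALT Grade 2 and worst bilirubin Grade 2, and so fall in the same cells. Only X meets criterion 2. Splitting by baseline status, liver metastasis or response does not separate them.

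**4. Search of the SAP for ECIs.** SAP 11.1.3 has 27 overview rows, 23 summaries by system organ class and preferred term, and 8 additional listings. None is for ECIs. No output in SAP 11.4 joins ALT/AST and bilirubin by date. SAP 4.3 nevertheless records no discrepancies from the protocol.

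**The case against.** The strongest reply is that Arm C is far from uncovered, and much of it stands.

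- **Reporting.** An important medical event may be classed as an SAE in any arm (Protocol 7.1.5), and SAEs go out within 24 h (7.2.3). The DLT list has a clause for any hazardous toxicity at any time. The Dose Escalation Committee reviews Arm C safety data before cohort 5 starts and again after its first three subjects. These are real safeguards, but for a non-serious laboratory rise the SAE and DLT clauses act only by judgement.
- **Tabulation.** Clinically relevant laboratory abnormalities are AEs (7.2.2) and enter the TEAE tables. DLTs are counted for Arm C. Liver parameters are tabulated by liver metastasis, and all laboratory values are listed. With 9 planned subjects, coincident rises can be found by reading the listings. This is fair, but a reader of the tables alone cannot find them.
- **Unseen documents.** Table shells and the Cohort Management Plan are separate documents, so the absence is shown only for the SAP text.

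A reader might infer that such a rise in Arm C is neither expedited nor tabulated. The routes above contradict that. A reader might also infer that the ECI rule has no effect in Arm C. Only the heading says so; the body of 7.2.1.1, 7.2.1 and 5.6 point the other way, so this is an ambiguity and not a proven exclusion.

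**Conclusion.** The point holds in a limited form. The protocol disagrees with itself on which arms the ECI definition and its 24 h rule cover. In Arm C, a non-serious concurrent rise that meets criterion 2 but is below the combined DLT thresholds, after Cycle 1 or judged unrelated has no unambiguous mandatory 24 h route. The SAP text counts ECIs in no arm, and its hepatotoxicity tables cannot distinguish simultaneous from separate elevations.

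The clearest exposure is the 9 planned Arm C subjects. It might be read as covering every monotherapy subject, but prospective reporting cannot help Phase I, completed in August 2021, and Arm D stopped after one subject (SAP 6.1, footnote 1). How many subjects would meet criterion 2 cannot be derived from the documents. The worked example assumes normal baseline values for its grades. This is a cheap improvement to a primary safety analysis, not a flaw that undermines the trial.

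**What to change.** 1. **Protocol.** The sponsor should reconcile 5.6, 7.2.1 and the heading and body of 7.2.1.1 on which arms the ECI definition and 24 h rule cover. The choice of arms and of any clinical threshold is the sponsor's.
2. **SAP 11.1.3.** Add an ECI row for the arms covered.
3. **SAP 11.4.** Add, by cohort/arm, the number and a listing of subjects whose AST/ALT, total bilirubin and ALP meet the protocol's own criterion 2 on the same sample date. Show baseline values and baseline liver-metastasis status. This matters because inclusion criterion 19 allows AST/ALT up to 5 x ULN with liver metastases, so a subject can enter already above the 3 x ULN component. Bilirubin is capped at 1.5 x ULN except in familial bilirubinemia, which limits flags present from the start.

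Item 3 uses laboratory data already collected and does not depend on how item 1 is settled. The cost is one derived table with its listing, and some flags that reflect disease and not treatment. If the sponsor confirms ECI scope for all arms, expect a few extra 24 h reports and a protocol amendment, with ethics committee and authority approval if it is substantial (Protocol 10.6).

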7.2.1.2 Treatment of Overdose (Arm B)

For this study, an overdose of pembrolizumab will be defined as any dose of 1000 mg or greater.

No specific information is available on the treatment of overdose of pembrolizumab. In the event of overdose, the subject should be observed closely for signs of toxicity. Appropriate supportive treatment should be provided if clinically indicated.

7.2.1.3 Time Period and Frequency for Collecting AE, SAE and Other Reportable Safety Event Information (Arm B)

Specific considerations on safety reporting for Arm B are summarized below:

- All AEs, SAEs and other reportable safety events that occur after the consent form is signed but before treatment /allocation must be reported by the investigator if the participant is receiving placebo run-in or other run-in treatment, if the event cause the participant to be excluded from the study, or is the result of a protocol-specified intervention, including but not limited to washout or discontinuation of usual therapy, diet, or a procedure.
- All AEs or ECIs (Events of Clinical Interest) from the time of treatment/ allocation through 30 days following cessation of study treatment must be reported by the investigator.
- All AEs meeting serious criteria, from the time of treatment/ allocation through 90 days following cessation of study treatment, or 30 days following cessation of study treatment if the participant initiates new anticancer therapy, whichever is earlier must be reported by the investigator.
- All pregnancies and exposure during breastfeeding, from the time of treatment/ allocation through 120 days following cessation of study treatment, or 30 days following cessation of study treatment if the participant initiates new anticancer therapy must be reported by the investigator.
- Additionally, any SAE brought to the attention of an investigator at any time outside of the time period specified above must be reported immediately to the Sponsor if the event is considered to be drug-related.

